1. INTRODUCTION

1.1. Background

Coronaviruses are spherical, enveloped viruses with positive-sense single-stranded RNA genomes. One fourth of their genome is responsible for coding structural proteins, such as the spike glycoprotein, envelope, membrane, and nucleocapsid proteins. Envelope, membrane, and nucleocapsid proteins are mainly responsible for virion assembly, while the spike protein is involved in receptor binding, mediating virus entry into host cells during coronavirus infection via different receptors (Li 2016).

Severe Acute Respiratory Syndrome Corona Virus 2 is a coronavirus responsible for the current COVID-19 global pandemic. SARS-CoV-2 belongs to the phylogenetic lineage B of the genus Beta-coronavirus and it recognizes the ACE2 as the entry receptor (Zhou et al 2020). Several new SARS-CoV-2 variants have been identified: the Alpha variant (B.1.1.7), the Beta variant (B.1.351), the Gamma variant (P.1), the Delta variant (B.1617.2) and the Omicron variant (B.1.1.529) (US CDC 2021; US CDC 2022; WHO 2021). These variants contain multiple spike protein mutations and mutations in other genomic regions.

AZD7442 is a combination product of two mAbs (AZD8895 and AZD1061) directed against RBD of the SARS-CoV-2 spike protein for neutralization of the virus. The two component mAbs bind unique, non-overlapping epitopes on the RBD of the viral spike protein. The use of two such mAbs provides redundancy in protection in case of virus mutation and escape. In response to the emergence of the B.1.1.7 and B.1.351 SARS-CoV-2 strains, preliminary in vitro neutralization assays demonstrated that the two component mAbs neutralized both emergent strains.

AZD8895 and AZD1061 mAbs have been engineered with triple amino acid substitutions (YTE) in the Fc region to prolong the half-life, which is expected to confer protection from COVID-19 for a duration of at least 5 months. An additional triple amino acid substitution (TM) in the Fc region was engineered for both AZD8895 and AZD1061 to reduce Fc mediated effector function, which is expected to reduce theoretical risk of antibody-dependent enhancement of disease. Importantly, incorporation of these YTE and TM substitutions did not alter the neutralization potency of AZD7442 in vitro.

A detailed description of the chemistry, pharmacology, efficacy, and safety of AZD7442 is provided in the IB.

1.2. Rationale for Conducting this Study

The study will assess PK comparability between different formulations of AZD7442, which is a combination of two individual mAbs, AZD8895 and AZD1061, and the individual formulations for each mAb. The materials to be assessed will be:

- A co-formulation of clonal cell line material of AZD8895 + AZD1061 mAbs as a single IM injection from a single mixture,
- Individual formulations of clonal cell line material of AZD8895 and AZD1061 mAbs as separate sequential IM injections, and
- Individual formulations of cell pool material of AZD8895 and AZD1061 mAbs as separate sequential IM injections.

2. STUDY OBJECTIVES

2.1. Primary Objectives

Table 2-1 Primary Objective and Outcome Measures

Primary Objectives	Outcome Measures

To evaluate the PK comparability between AZD7442 administered as a single IM dose (co-formulation) (AZD8895 + AZD1061) and two separate IM doses (AZD8895 and then AZD1061) (clonal cell line material of AZD8895 and AZD1061) of the individual mAbs in healthy adult participants	
AUC_{inf}, AUClast, and C_{max}

To evaluate the PK comparability between AZD7442 administered as single IM dose (co-formulation) (AZD8895 + AZD1061) and two separate IM doses (AZD8895 and then AZD1061) (cell pool material of AZD8895 and AZD1061) of the individual mAbs in healthy adult participants	
AUC_{inf}, AUClast, and C_{max}

To evaluate the PK comparability between the clonal cell line material and the cell pool material of AZD7442 administered as two separate sequential IM doses (AZD8895 and then AZD1061) of the individual mAbs in healthy adult participants	
AUC_{inf}, AUClast, and C_{max}

Abbreviations: AUC: area under the serum concentration-time curve; C_{max}: maximum observed serum (peak) concentration; IM: intramuscular; mAbs: monoclonal antibodies; PK: pharmacokinetic.

2.2. Secondary Objectives

Table 2-2 Secondary Objectives and Outcome Measures

Secondary Objectives	Outcome Measures

To examine the serum PK profiles of AZD7442 when administered as a single IM dose (co-formulation) (AZD8895 + AZD1061) and as two separate IM doses (AZD8895 and then AZD1061) (clonal cell line or cell pool material) of the individual mAbs in healthy adult participants	
T_{max}, AUC_{0-31d}, AUC_{0-61d}, AUC_{0-91d}, AUC_{0-181d}, t_{last}, t_{½λz}, CL/F, and V_z/F

Secondary Objectives	Outcome Measures

 To further assess the safety of AZD7442 when administered as a single IM dose (co-formulation) (AZD8895 + AZD1061) and two separate IM doses (AZD8895 and then AZD1061) (clonal cell line or cell pool material) of the individual mAbs in healthy adult participants 	
 AEs including serious AEs and AEs of special interest Laboratory assessments (hematology, clinical chemistry, and urinalysis) Physical examination Electrocardiogram Vital signs (systolic and diastolic blood pressure, pulse rate)

 To evaluate the ADA responses to AZD7442 in serum following administration a single IM dose as a co-formulation (AZD8895 + AZD1061) and as two separate IM doses (AZD8895 and then AZD1061) (clonal cell line or cell pool material) of the individual mAbs in healthy adult participants 	
 Incidence and titers of anti-AZD8895 and anti-AZD1061 antibodies

Abbreviations: AE: adverse events; AUC: area under the serum concentration-time curve; CL/F: apparent clearance after extravascular administration; IM: intramuscular; PK: pharmacokinetic; $t_{1/2}\lambda_z$: terminal elimination half-life; tlast: time of last quantifiable concentration; Tmax: time to maximum observed serum concentration; Vz/F: volume of distribution based on terminal phase after extravascular administration.

2.3. Exploratory Objectives

Table 2-3 Exploratory Objectives and Outcome Measures

Exploratory Objectives	Outcome Measures

 CC1 	
 CC1

Abbreviation: IM: intramuscular.

Refer to Section 10.2 for PK variables, Section 6.3 for safety variables.

3. STUDY DESIGN

3.1. Overall Study Design and Flow Chart

This study will be an open label, randomized, three-arm, parallel group, single dose, study in healthy participants (males and females), performed at multiple study centers.

A total of 207 evaluable healthy male and female participants will be randomized in a 1:1:1 ratio between the three treatment groups (69 participants per group). Each participant will receive AZD7442 as either a single IM dose (co-formulation; AZD8895 + AZD1061) from a single vial or as two separate IM doses of the individual mAbs (AZD8895 and then AZD1061) from two separate vials from either clonal cell line material or cell pool material as follows:

- **Treatment A:** 300 mg (total protein) AZD7442 as a single IM dose (co-formulation of 150 mg AZD8895 + 150 mg AZD1061) (clonal cell line material).
- **Treatment B:** 300 mg (total protein) AZD7442 as two separate IM doses of the individual mAbs (150 mg AZD8895 and then 150 mg AZD1061) (clonal cell line material).
- **Treatment C:** 300 mg (total protein) AZD7442 as two separate IM doses of the individual mAbs (150 mg AZD8895 and then 150 mg AZD1061) (cell pool material).

The product in Treatment Groups A and B is derived from material that originated from a clonal cell line, with a separate cell line, GMP cell bank, and manufacturing process for AZD8895 and AZD1061. The product in Treatment Group C is derived from material that originated from a non-clonal cell pool, with a separate pool of cells, GMP cell bank, and manufacturing process for AZD8895 and AZD1061. The clonal cell line is derived from a subpopulation of the respective cell pool, and there are no differences in antibody sequence between these cell banks. These materials have been demonstrated to be analytically comparable to each other. Refer to [Table 5-1](#) for details on the IMP.

Additionally, within each of the treatment groups, participants will be randomized 1:1:1 to one of the three injection sites:

- Lateral thigh,
- Gluteal dorsal,
- Gluteal ventral.

Further, participants will be stratified based on the body weight and vaccination status at randomization as follows:

[figure not shown]
- Body weight at randomization: < 70 kg; 70 to < 80 kg; and \geq 80 kg
- Anti-SARS-CoV-2 vaccination status at randomization: non-vaccinated or vaccinated (with one or more locally approved/authorized COVID-19 vaccine doses)

The study will comprise of:

- A Screening Period of up to 28 days that requires participants to visit the Clinical Unit (Visit 1).
- A Treatment Period of 1 day (Day 1; Visit 2) during which participants will be admitted to the study Clinical Unit and be randomized to receive their dose of IMP (AZD7442 as either a single IM dose or two separate IM doses). Participants will stay at the study clinic for at least 8 hours after dosing and will be discharged from the Clinical Unit at the discretion of the investigator, on the same day.
- A Follow-up Period of approximately 1 year consisting of regular visits to the study Clinical Unit starting from the day after dosing, Day 2 through to Day 361. The subsequent study visits total in 11 outpatient follow-up visits (Visits 3 to 13).

Details of IMP administration are provided in Section [5.4.6](#).

Figure 3-1 Study Flow Chart

Abbreviation: IM: Intramuscular

Treatment A: 300 mg IM coformulation in one injection of 2 mL (clonal cell line material)

Treatment B: 300 mg IM from individual vials, 2 injections of 1.5 mL (clonal cell line material)

Treatment C: 300 mg IM from individual vials, 2 injections of 1.5 mL (cell pool material)

Table 3-1 Schedule of Assessments: Screening, Randomization, and IMP Administration

Procedures	Screening Period		Treatment Period	
	Day -28-to -1			
	Visit 1	Visit 2		
Written informed consent and assignment of enrollment code	X			
Medical history	X		X ^a	
Demographics	X			
Full physical examination, height, weight, and BMI	X		X ^a	
12-Lead ECG	X		X	
Vital signs	X		X	
Serum chemistry ^b	X		X	
Hematology ^b	X		X	
Coagulation ^b	X		X	
Urinalysis ^b	X		X	
FSH (postmenopausal women only) ^{b,c}	X			
Pregnancy test (serum β-hCG) ^c	X			
Pregnancy test (urine dipstick) ^{c,d}			X	
HIV, hepatitis B, hepatitis C testing	X			
Urine drug and alcohol screen ^{b,e}	X		X	
Assessment of AEs/SAEs ^f	X		X	
Concomitant medications	X		X	
Verify eligibility criteria	X		X	
Anti-COVID-19 vaccination status ^g	X		X	
Monitoring for COVID-19 symptoms and exposure history	X		X	
Documented SARS-CoV-2 RT-PCR test taken ≤ 3 days before Day 1 OR Rapid SARS-CoV-2 antigen test (for screening criteria) ^h			X	
SARS-CoV-2 serology ⁱ			X	
Randomization			X	
Participant identification card			X	
AZD7442 administration ^j			X	
Injection site monitoring			X	

Procedures	Screening Period	Treatment Period
Study Day	Day -28-to -1	Day 1
Study Visit	Visit 1	Visit 2
Serum sample for AZD7442 PK ^k		X
Serum sample for anti-AZD7442 antibodies ^l		X
Serum sample for CCI [REDACTED] ^m		X
AstraZeneca Thank you Card		X

- ^a Update of the screening medical history and physical examination (any new findings since screening).
- ^b Serum chemistry, hematology, coagulation, FSH, urinalysis, urine drug, and alcohol screen do not need to be repeated on Day 1 as per investigator's discretion, if they were performed within 2 days prior to Day 1. Serum chemistry, hematology and coagulation may be repeated only once during Screening period, if values at Screening visit were outside of reference range and documented as not clinically significant.
- ^c Female participants only. Pregnancy test must be negative at screening as well as before randomization and study drug administration.
- ^d Urine dipstick pregnancy test will be done on female participants of childbearing potential only (not postmenopausal female participants that will be identified based on FSH test).
- ^e On Day 1, alcohol breathalyzer test needs to be performed before randomization if urine alcohol screen was done more than 2 days before Day 1. If alcohol breathalyzer test is positive, participant cannot be included in the study.
- ^f SAE data will be collected from screening until Day 361. AE data will be collected from Day 1 until Day 361.
- ^g Participants will be asked about anti-COVID-19 vaccination status. Participants should be either non-vaccinated or vaccinated (with one or more locally approved/authorized COVID-19 vaccine dose) with the last dose of the vaccine received at least 14 calendar days before Day 1. Vaccination status will be entered into IRT/RTSM during randomization on Day 1 visit to allow for balanced recruitment.
- ^h SARS-CoV-2 RT-PCR test or a rapid SARS-CoV-2 antigen test will be done at a local laboratory/site. If a documented SARS-CoV-2 RT-PCR test is not available at screening, a rapid SARS-CoV-2 antigen test will be performed on the day of randomization, pre-dose (for screening criteria). Either test must be negative before dosing.
- ⁱ SARS-CoV-2 serology analysis will be done at the central laboratory for all participants.
- ^j Participants will be randomized in a 1:1:1 ratio by site of injection to receive the IM dose of the IMP in the lateral thigh, gluteal dorsal or gluteal ventral. This information will be provided to the investigator via IRT/RTSM. Participant should be monitored for injection site reaction on Day 1.
- ^k On Day 1 PK samples will be collected at pre-dose, and then 2 h, 4 h, and 8 h post dosing; on Day 2 PK sample will be collected 24 h post dosing.
- ^l On Day 1 sample will be collected as pre-dose only.
- ^m On Day 1 samples will be collected as pre-dose and then 2 h and 4 h post dosing; on Day 2 sample will be collected 24 h post dosing.

Abbreviations: AE: adverse event; β -hCG: beta human chorionic gonadotropin; BMI: body mass index; ECG: electrocardiogram; FSH: follicle-stimulating hormone; HIV: human immunodeficiency virus; IRT/RTSM Interactive Response Technology/Randomization and Trial Supply Management; PK: pharmacokinetics; SAE: serious adverse events; RT-PCR: reverse transcriptase polymerase chain reaction; SAE: serious adverse event; SARS-CoV-2: Severe Acute Respiratory Syndrome Corona Virus 2.

Table 3-2 Schedule of Assessments: Follow-up Period

Procedures	Follow-up Period										
Study Day	Day 2	Day 5 ±1 day	Day 8 ±1 day	Day 15 ±1 day	Day 22 ±2 days	Day 31 ±2 days	Day 61 ±5 days	Day 91 ±5 days	Day 181 ±5 days	Day 271 ±7 days	Day 361/ET ±7 days
Study Visit	Visit 3	Visit 4	Visit 5	Visit 6	Visit 7	Visit 8	Visit 9	Visit 10	Visit 11	Visit 12	Visit 13
Full physical examination, height, weight, and BMI			X			X					X
12-Lead ECG		X	X			X					X
Vital signs		X	X			X					X
Serum chemistry		X	X			X					X
Hematology		X	X			X					X
Coagulation		X	X			X					X
Urinalysis		X	X			X					X
Pregnancy test (urine dipstick) ^a	X	X	X	X	X	X	X	X	X	X	X
Assessment of AEs/SAEs	X	X	X	X	X	X	X	X	X	X	X
Concomitant medications	X	X	X	X	X	X	X	X	X	X	X
Anti-COVID-19 vaccination status ^b	X	X	X	X	X	X	X	X	X	X	X
Monitoring for COVID-19 symptoms and exposure history	X	X	X	X	X	X	X	X	X	X	X
Serum sample for AZD7442 PK	X	X	X	X	X	X	X	X	X	X	X
Serum sample for anti-AZD7442 antibodies						X		X	X		X
Serum sample for CCI [REDACTED]	X		X			X	X	X	X	X	X
SARS-CoV-2 serology	X		X			X	X	X	X	X	X

^a For female participants only. Pregnancy test should be negative for continued participation in the study.

^b Participants will be allowed to receive anti-COVID-19 vaccination during the study, however, should wait 14 days after their dose of AZD7442, and will be asked about the vaccination status at each visit. Participant vaccination status will be documented throughout the study in the eCRF.

Abbreviations: AE: adverse event; BMI: Body mass index; COVID-19: coronavirus disease 2019; ECG: electrocardiogram; ET: Early Termination; SAE: serious adverse event; PK: pharmacokinetics; SARS-CoV-2: Severe Acute Respiratory Syndrome Corona Virus 2.

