4.2.1.3. Male Participants

Restrictions for Male Participants

There is no information about effects that AZD7442 could have on the development of the fetus in humans.

All male participants should avoid the transfer of any fluids to a sexual partner by using a condom from the day of IMP administration (Day 1) up to 90 days following IMP administration. Female partners of male participants should be either of non-childbearing potential or should use a highly effective contraception form of birth control as mentioned in Section [4.2.1.2](#) above, from the day of IMP administration (Day 1) up to 90 days following IMP administration.

Sperm Donation

Male participants should not donate sperm for the duration of the study until after the last study Follow-up Visit.

Pregnancy

Participants will be instructed that if their partner becomes pregnant during the study this should be reported to the investigator. The investigator should also be notified of pregnancy occurring during the study but confirmed after completion of the study. In the event that a participant's partner is subsequently found to be pregnant after the volunteer is included in the

study, then consent will be sought from the partner and if granted any pregnancy will be followed and the status of mother and/or child will be reported to the sponsor after delivery.

A pregnancy notification form and follow-up will be completed.

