5.2. Procedures for Handling Incorrectly Randomized Participants

Participants who fail to meet the inclusion criteria or meet any exclusion criterion should not, under any circumstances, be randomized into the study. There can be no exceptions to this rule.

Where a participant, who does not meet the selection criteria, is randomized in error and this is identified before dosing, the participant should be withdrawn from the study. If a participant is withdrawn prior to dosing they will be replaced.

If a participant, who does not meet the selection criteria, has been dosed before the error is identified, the participant should be advised to continue follow-up visits and safety assessments to ensure their safety. The investigator will inform the AstraZeneca Lead Physician of the error immediately.

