5.4.5. Dose and Treatment Regimens

Each participant will receive a single IM dose of AZD7442 on Day 1 after randomization to one of the three treatment groups ([Table 5-2](#)). Additionally, within each of the treatment groups, participants will be randomized 1:1:1 to injection sites of lateral thigh (vastus lateralis), gluteal dorsal, or gluteal ventral.

Participants receiving Treatment A will be administered a dose via a single IM injection from a single drug product vial.

Participants receiving Treatment B or Treatment C will be administered a dose via two separate IM injections, each from a separate drug product vial containing AZD8895 or AZD1061. AZD8895 is administered first, followed by AZD1061. If a participant experiences an immediate hypersensitivity reaction after receipt of the first IM injection, but before the second IM injection, further IMP should not be given.

Participants will be allowed to drink water until 45 min to 1 hour before dosing to prevent dehydration. Water and food will be allowed ad libitum from 1 hour after the start of dosing.

After dosing, participants will remain semi-supine on their bed or sitting (except when necessary for study procedures) until completion of the Day 1 assessments.

Other restrictions, including posture control are described in Section 4.2. Data of participants may be excluded from the PK analysis set as described in Section 11.1.3.

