5.7. Discontinuation of Study Intervention and Withdrawal from Study

Healthy participants may be discontinued from IMP in the following situations:

- Healthy participant decision. The healthy participant is at any time free to discontinue treatment, without prejudice to further treatment.
- Severe non-compliance to study protocol.
- Any significant and clinically relevant changes in the safety parameters (eg, ECG, BP, pulse, laboratory assessments and AE) making the continuation of IMP administration unjustified.
- Any case of PHL according to [Appendix C](#).

The appropriate AE form in the CRF must be completed.

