6.3.1.3. Adverse Events of Special Interest

Adverse events of special interest are events of scientific and medical interest, specific to the further understanding of the study intervention safety profile and require close monitoring and rapid communication by the investigators to the sponsor. An AESI can be serious or non-serious. All AESIs will be recorded in the eCRF. Serious AESIs will be recorded and reported as per Section [6.3.1.6](#). See also the AZD7442 IB for additional information on AESIs.

The AESIs for AZD7442 are:

- Anaphylaxis and other serious hypersensitivity reactions, including immune complex disease
- Injection site reactions
- Cardiac ischemia, cardiac failure, and thrombotic events

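### Table 3-2 footnote a ties continued participation to a negative pregnancy test after the only dose, which prevents no exposure and can end recorded AE/AESI follow-up early (minor)

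*Protocol*

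**What the plan says.** - **Dosing.** Protocol Section 5.4.5: "Each participant will receive a single IM dose of AZD7442 on Day 1 after randomization". No dose follows.
- **Before dosing.** Protocol Table 3-1, footnote c: "Pregnancy test must be negative at screening as well as before randomization and study drug administration".
- **After dosing.** Protocol Table 3-2 schedules a urine dipstick at all 11 follow-up visits, Day 2 to Day 361. Footnote a to that row: "Pregnancy test should be negative for continued participation in the study".
- **Planned AE collection.** Protocol Table 3-1, footnote f: "AE data will be collected from Day 1 until Day 361".
- **Dosed but ineligible participants.** Protocol Section 5.2: "the participant should be advised to continue follow-up visits and safety assessments to ensure their safety".
- **Discontinuation list.** Protocol Section 5.7 opens with "Healthy participants may be discontinued from IMP in the following situations" and gives four situations. Pregnancy is not among them.
- **After exit.** Section 5.7.1 asks for an Early Termination visit if possible and mentions modified follow-up options. Section 6.3.1.5 has unresolved AEs followed medically, but outside the eCRF. Sections 4.2.1.2, 12.3 and 12.3.1 require pregnancy reporting and outcome follow-up, including after discontinuation.

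**The concern.** A negative-test condition makes sense before a dose. After the only dose there is nothing left to withhold, so the condition cannot protect the participant or the fetus from exposure. With the half-life of about 90 days in Protocol Section 3.3.2, she stays exposed for months whether or not she remains in the study.

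What the condition can do is stop the scheduled questions about new AEs, and their recording in the eCRF, in someone already exposed. Section 6.3.1.3 says that AESIs, which include thrombotic events, "require close monitoring and rapid communication by the investigators to the sponsor". Section 4.2.1.3 adds: "There is no information about effects that AZD7442 could have on the development of the fetus in humans". The AE record of an exposed pregnant participant is therefore worth keeping. At stake is the completeness of safety follow-up in a very small number of people.

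**Working it through.** The plan gives no figure on this point to reproduce. The check compares the provisions, then counts what would be lost.

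**1. The provisions, by case**

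| Case | Footnote a | Other provisions |
|---|---|---|
| Pregnant at dosing, test missed it | Participation should not continue | Pregnancy is exclusion criterion 15 (Section 4.1.2), so Section 5.2 applies and advises continued visits and safety assessments. The two conflict. |
| Conceived after dosing | Participation should not continue | No sentence says that she stays in scheduled visits. Section 5.7 does not list pregnancy as a reason to stop. |

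**2. Loss by visit of the first positive test**

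Days lost = 361 − visit day. Later visits are counted from Table 3-2 (AE assessment at every visit; ADA at Days 31, 91, 181 and 361). Drug remaining = 2^(−(day − 1)/90), a simple first-order decline from Day 1 that ignores absorption.

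| Positive at | AE days lost | Later AE visits | Later ADA visits | Drug remaining |
|---|---|---|---|---|
| Day 31 | 330 | 5 | 3 | 79% |
| Day 61 | 300 | 4 | 3 | 63% |
| Day 91 | 270 | 3 | 2 | 50% |
| Day 181 | 180 | 2 | 1 | 25% |
| Day 271 | 90 | 1 | 1 | 12.5% |
| Day 361 | 0 | 0 | 0 | 6% |

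Doses avoided by exit: none in any row. An Early Termination visit, if held, gives back one AE assessment, one PK sample and one ADA sample. It takes place at exit, so it does not cover the days that follow.

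**3. Average loss per case**

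Assumptions: conception is equally likely on each of the 360 days after dosing, the dipstick turns positive 14 days after conception, and detection is at the next scheduled visit. A positive test at Day 15 or earlier then means conception on or before Day 1, which is the Section 5.2 case. Post-dose conceptions are first detected at Day 22.

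- Sum of days lost: 7×339 + 9×330 + 30×300 + 30×270 + 90×180 + 90×90 = 46,743.
- Conceptions detected at Day 361, or not detected by then (90 + 14 days), lose nothing.
- Mean over all cases: 46,743 / 360 = 130 days.
- Share with any loss: (7 + 9 + 30 + 30 + 90 + 90) / 360 = 256/360 = 71%.

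With detection at the first visit after conception and no lag, the figures would be 51,651/360 = 143 days and 270/360 = 75%. The lagged figures are the more realistic.

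**4. Expected number affected**

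The documents do not give the number of women of childbearing potential; 50 to 100 is assumed. The rate of about 1% per year comes from Section 4.2.1.2, which states less than 1% for consistent and correct use.

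- Expected pregnancies: 0.01 × 360/365 × (50 to 100) = 0.49 to 0.99.
- Expected with lost follow-up: × 256/360 = 0.35 to 0.70.
- Chance that nobody is affected (Poisson): exp(−0.35) = 70% to exp(−0.70) = 50%.

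The extra barrier method in Section 4.2.1.2 would lower these numbers; imperfect use would raise them.

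**The case against.** The strongest reply is that the protocol does not compel removal. Footnote a says *should*, whereas the pre-dose footnote says *must*. Section 5.7 omits pregnancy, Section 5.7.1 leaves withdrawal by the investigator to discretion, and the AE collection window has no pregnancy exception. Section 12.3.1 requires outcome follow-up even where the participant was discontinued, which suggests that discontinuation is not automatic. All of this stands and keeps the point small. It does not tell a site to keep a participant who conceives after dosing, so sites could differ.

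A second reply is that a reader might infer that safety follow-up stops altogether. The documents do not support that. An Early Termination visit is requested. Modified follow-up, such as telephone contact, is possible, although Section 5.7.1 offers it to a participant who is considering withdrawal. The PREGREP and PREGOUT modules record the pregnancy and its outcome, the status of mother and/or child is reported after delivery, abnormal outcomes are SAEs, and related SAEs that come to the investigator's attention are still reported. Information on the fetus comes mainly through these routes. The loss is scheduled, eCRF-recorded questioning about new AEs and AESIs, and the later samples.

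A third reply is that ending research visits and blood draws in pregnancy is a defensible choice. That is fair for blood draws, so they should be optional. It is a weaker reason to stop asking about AEs. The consent pages are not available, so whether they address this cannot be checked.

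**Conclusion.** The point holds as a minor patient-safety matter. Footnote a prevents no exposure. If applied, it cuts short recorded AE/AESI follow-up in a participant who conceives after dosing, and it contradicts Section 5.2 for a pregnancy already present at dosing. Under the stated assumptions about 71% of cases lose follow-up, with a mean of about 130 days over all cases, and probably zero or one participant is affected.

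Three stronger readings should be resisted:

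- A reader might infer that sites have only footnote a to go by. Section 5.2 with exclusion criterion 15 covers a pregnancy present at dosing.
- A reader might treat 1% per year as a ceiling on pregnancies. It applies to consistent and correct contraceptive use and is not a strict upper bound.
- A reader might infer harm to the PK comparison. With zero or one early exit expected in a trial with 69 participants per arm, nothing supports a claim about power, bias between arms or the PK conclusions.

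**What to change.** Replace the second sentence of Table 3-2 footnote a with:

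> A positive test is reported under Section 12.3 and does not by itself end participation. AE/SAE/AESI collection continues to Day 361. PK and ADA samples are taken only if the participant agrees and the investigator considers it appropriate.

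Leave Table 3-1 footnote c unchanged.

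The cost is a short wording change in an amendment; the visits are already scheduled. The downside is continued visits, and possibly some optional blood draws, in a consenting pregnant participant. The protocol estimated completion in Q3 2023 and the SAP is dated 27 October 2023. If follow-up has ended, the useful step is to check whether anyone left on a positive test and to correct the wording in later single-dose protocols.
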